## 9. STUDY MANAGEMENT BY ASTRAZENECA OR REPRESENTATIVE

# 9.1 **Pre-study activities**

Sites that the TIMI study organisation, the Hadassah Medical Center, BMS and/or AstraZeneca have had previous experience with will participate in the study. A determination of the suitability of the Investigator site will be made mainly based on historical performance and confirmatory telephone contact with site personnel. In rare cases, such as where the site personnel are markedly changed, further examination may be needed. The information on the site suitability will be documented.

# 9.2 Training of study site personnel

A representative of the TIMI study organisation, of the Hadassah Medical Center or an AstraZeneca or other representative will review and discuss the requirements of the Clinical Study Protocol and related documents with the investigational staff and also train them in any study-specific procedures and the electronic systems utilised.

# 9.3 Monitoring of the study

Monitoring of the site, site documents and data will be limited.

Site visits will comprise about 1 or 2 visits per year unless "for cause".

The monitor will confirm the following:

- There is a complete patient file for each patient enrolled in the study.
- There is an informed consent for the patient and this consent process has been administered correctly.

The monitor will review the patient file to ensure that all study endpoints (ie, the composite endpoint of CV death, non-fatal MI or non-fatal ischaemic stroke and other secondary endpoints) have been recorded onto the CRF and that the adjudication packets are complete. Likewise, the monitor will review all AEs or SAEs that have been recorded on the CRF. Also key is the need to ensure all events and data pertaining to "adverse events of special interest" are adequately captured.

At the time of the monitor visit, it is appropriate to discuss the study progress with site personnel to confirm all processes and procedures in the protocol are being adhered to correctly, data in the CRF's are being recorded in a timely manner, biological and/or genetic samples are being handled correctly, and IP accountability checks are being performed.

## 9.3.1 Source data

For location of source data, see the Clinical Study Agreement.

# 9.4 Study agreements

The PI at each centre should comply with all the terms, conditions, and obligations of the Clinical Study Agreement for this study. In the event of any inconsistency between this Clinical Study Protocol and the Clinical Study Agreement, the terms of Clinical Study Protocol shall prevail with respect to the conduct of the study and the treatment of patients and in all other respects, not relating to study conduct or treatment of patients, the terms of the Clinical Study Agreement shall prevail.

Agreements between AstraZeneca or its representative and the PI should be in place before any study-related procedures can take place or patients are enrolled.

### 9.4.1 Archiving of study documents

The Investigator follows the principles outlined in the Clinical Study Agreement.

## 9.5 Study timetable and end of study

The end of the study is defined as "the date of the last visit of the last patient undergoing the study."

The study is expected to start in Q2 to Q3 2010 and to end by Q3 2014 to Q2 2015.

However, as the study is event driven, the accrual of the predetermined number of events included in the composite endpoint of CV death, non-fatal MI or non-fatal ischaemic stroke will finally determine the duration of the study.

The study may be terminated at individual centres if the study procedures are not being performed according to GCP, or if recruitment is slow. AstraZeneca may also terminate the entire study prematurely if concerns for safety arise within this study or in any other study with saxagliptin.

The study can also be stopped at the interim analysis for efficacy (see Section 12.2.4).

## **10. DATA MANAGEMENT BY ASTRAZENECA OR DELEGATE**

Data management will be performed by AstraZeneca Data Management Centre staff.

The data collected through third-party sources will be obtained and reconciled against study data.

AEs will be classified according to the terminology of the latest version of the MedDRA. Medications will be classified according to the AstraZeneca Drug Dictionary. All coding will be performed by AstraZeneca Data Management Centre staff, with the exception of SAE coding, which will be completed by BMS.

Data queries will be raised for inconsistent, impossible or missing data. The data will be validated as defined in the Data Management Plan. Quality control procedures will be applied to each stage of data handling to ensure that all data are reliable and have been processed correctly.

When all data have been coded, validated, signed and locked, a clean file will be declared. Any treatment revealing data may thereafter be added and the final database will be locked.

Each individual electronically signing electronic CRFs must meet AstraZeneca training requirements and must only access the AstraZeneca electronic data capture tool using the unique user account provided by AstraZeneca or their designee. User accounts are not to be shared or reassigned to other individuals.

Laboratory and IVRS/IWRS data will be electronically transferred to AstraZeneca. The processes will be documented in the Data Management Plan, and the validation performed under the direction of the responsible Data Manager, according to the data validation plan.

In the case of genotype data, only the date the patient gave consent to participation in the genetic research and the date the blood sample was taken from the patient will be recorded in the CRF and database. In the case of biological sample data, only the date the patient gave consent to participation in the biological sample research and the date the blood sample was taken from the patient will be recorded in the CRF and database.

The genotype data generated from the study will be stored in an appropriate secure system separate from the database used for the main study. Some or all of the dataset from the main study may be duplicated in this database for exploratory genetic analysis. The same is applicable for the biological sample research data.

Data associated with biological samples will be transferred to laboratories internal or external to AstraZeneca.

# 11. EVALUATION AND CALCULATION OF VARIABLES BY ASTRAZENECA

## **11.1** Calculation or derivation of efficacy variable(s)

The primary efficacy endpoint is the time to the first event included in the composite endpoint of CV death, non-fatal MI or non-fatal ischaemic stroke. For this endpoint and for the secondary time-to-event endpoints, the time from randomisation to event or time to last documented contact for patients with no event will be calculated.

A patient may have 1 or more events. However, only a patient's first occurring event will contribute to the analysis of the specified variable.

Only events adjudicated and confirmed by the CEC will be included in the primary and secondary time to CV event analyses.

Total days of hospitalisation will be calculated as the date of discharge from the hospital minus the date admitted to hospital + 1. For each patient, the baseline for glycaemic measures (eg, HbA1c) are defined as the last assessment before the first dose of double-blind study drug. Change from baseline to any randomised treatment period Month t is defined as follows:

*CMonth t* = *MMonth t* - *Mbaseline*, where:

- CMonth t is the change from baseline at Month t
- MMonth t is the measurement at Month t
- Mbaseline is the baseline measurement

# **11.2** Calculation or derivation of safety variable(s)

The baseline value of each safety laboratory test or physical exam endpoint is defined as the last assessment before the date and (where available) time of the first dose of double-blind study drug.

Change from baseline will be calculated using the same method as for glycaemic efficacy variables.

## **11.2.1** Derivation or calculation of outcome variables

The mean BP measurements (diastolic and systolic BP) will be computed by AstraZeneca for each patient at each visit.

Estimated GFR will be using the MDRD formula (Levy et al 2006),

Estimated GFR = 175 x standardized  $S_{cr}^{-1.154}$  x age-0.203 x 1.212 [if black] x 0.742 [if female]

## 11.2.2 Other significant adverse events

During the evaluation of the AE data, an AstraZeneca medically qualified expert will review the list of AEs that were not reported as SAEs or as AEs leading to discontinuation of IP. Based on the expert's judgement, significant AEs of particular clinical importance may, after consultation with the Global Patient Safety Physician, be considered other significant adverse events (OAEs) and reported as such in the CSR.

Examples of OAEs are marked haematological and other laboratory abnormalities, and certain events that lead to intervention (other than those already classified as serious), dose reduction or significant additional treatment.

# **11.3** Calculation or derivation of patient reported outcome variables

This will be presented in a separate statistical analysis plan (SAP).

- 11.4 Calculation or derivation of pharmacokinetic variables (Not applicable)
- 11.5 Calculation or derivation of pharmacodynamic variables (Not applicable)

# **11.6** Calculation or derivation of pharmacogenetic variables

Please see Appendix F.

# **11.7** Calculation or derivation of health economic variables

The number of hospitalisations and percent of patients hospitalised will be calculated and summarised for both study arms. In addition, the length of the stay (using the admission and discharge dates) between the two arms will be computed.

# **12.** STATISTICAL METHODS AND SAMPLE SIZE

# **12.1** Description of analysis sets

### 12.1.1 Efficacy analysis set

All patients used in the analyses of the primary and secondary objectives will belong to the ITT population. This population is defined as all randomised patients. The patients will be analysed according to the treatment group to which they were randomised (not to which treatment they actually received).

### 12.1.2 Safety analysis set

The safety population will be identical to the ITT population.

### 12.1.3 Endpoint definitions

All primary and secondary efficacy endpoint events are defined in Appendix G.

### 12.1.3.1 Primary efficacy and safety endpoint

The primary endpoint is the time to first event included in the composite endpoint of CV death, non-fatal MI or non-fatal ischaemic stroke, using events adjudicated and confirmed by the independent adjudication committee. This endpoint will be used to assess both the primary efficacy objective and the primary safety objective.

### 12.1.3.2 Secondary efficacy endpoint

The **first** secondary efficacy endpoint is the time to the first event included in the composite endpoint of CV death, non-fatal MI, non-fatal ischaemic stroke, hospitalisation for heart failure, hospitalisation for unstable angina pectoris or hospitalisation for coronary revascularisation.

#### The next secondary efficacy endpoint is time to any documented death.

### 12.1.3.3 Other efficacy endpoints

Other efficacy endpoints include the time to the first event for the first 11 bullet points:

- Addition of new antidiabetic medication or  $\geq 1$  step increase in dose for an oral antidiabetic drug or  $\geq 25\%$  increase in insulin dose which lasts for  $\geq 3$  months
- Start of insulin regimen which lasts for  $\geq 3$  months
- Hospitalisation for hypoglycaemia
- CV death
- Non-fatal MI

- Non-fatal ischaemic stroke
- Hospitalisation for heart failure
- Hospitalisation for unstable angina pectoris
- Hospitalisation for coronary revascularisation
- Primary endpoint composite (CV death, non-fatal MI or non-fatal ischaemic stroke) occurring during the first year of follow-up and after the first year
- Documented laser treatment due to development of and/or deterioration in diabetic retinopathy
- Diabetic renal disease progression (diabetic nephropathy) as assessed by the following parameters:
  - Reduction from baseline of the microalbumin/creatinine ratio
  - Categorical change from baseline in albuminuria (normoalbuminuria, microalbuminuria, and/or macroalbuminuria)
  - Doubling of serum creatinine levels
  - Initiation of chronic dialysis and/or renal transplant and/or a serum creatinine >6.0 mg/dL (> 530 μmol/L)
- The composite event of death, doubling of serum creatinine, initiation of chronic dialysis, renal transplant, or a serum creatinine > 6.0 mg/dL (> 530 µmol/L)

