#### 2.2.2 Other efficacy objectives

Other efficacy objectives are to determine whether treatment with saxagliptin compared with placebo when added to current background therapy in patients with type 2 diabetes mellitus will result in a reduction of:

- Need for increase in dose or addition of new antidiabetic medication
- Initiation of insulin therapy in patients not receiving insulin therapy at baseline
- Hospitalisation for hypoglycaemia
- The individual components of the primary endpoint (CV death, non-fatal MI or non-fatal ischaemic stroke)
- The individual additional components of the secondary efficacy endpoint (hospitalisation for any of the following: heart failure, unstable angina pectoris and coronary revascularisation)
- The primary composite endpoint (CV death, non-fatal MI or non-fatal ischaemic stroke) during the first year of follow-up and after the first year
- Retinal laser treatment due to development of and/or deterioration in diabetic retinopathy
- New and/or progression of diabetic nephropathy

• The composite event of death, doubling of serum creatinine, initiation of chronic dialysis, renal transplant, or a serum creatinine > 6.0 mg/dL (> 530 µmol/L)

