# **1.1 Myocardial Infarctions**

All myocardial infarctions (MIs) will be counted as events whether they represent the reason for the hospitalisation or occurred during a hospitalisation. In addition, they will be counted as events whether they occurred spontaneously or as the direct consequences of an investigation/procedure or operation. In order to meet the criteria as an endpoint, an MI must be distinct from the qualifying event (ie, re-infarction for a patient who qualified for the study based on recent MI). The definition of MI as an endpoint will take into account whether a patient had a recent MI or has undergone revascularisation with percutaneous coronary invention (PCI) or coronary artery bypass graft (CABG) surgery. In cases where both cardiac troponin and CK-MB are available (drawn at similar time points) and are discordant, biomarker criteria will be applied using cardiac troponin. The definitions of MI are as follows for the 4 clinical settings in which it may occur:

A. **Spontaneous MI (normal biomarkers)** - For patients with no recent revascularisation in whom biomarkers were never elevated or have been documented to return to normal after a qualifying (or recent) MI, criteria 1 and 2 or criterion 3 or criterion 4 must be met:

- 1. Typical cardiac biomarker rise and/or fall with the following degrees of elevation accepted as biochemical evidence of myocardial necrosis (either one or both):
  - Troponin T or I: maximal concentration greater than the MI decision limit
  - CK-MB: maximal concentration greater than the ULN

AND

- 2. At least 1 of the following additional supportive criteria:
  - (a) Ischaemic discomfort at rest lasting >10 minutes or
  - (b) ECG changes indicative of ischaemia (ST elevation > 0.1 mV or ST depression > 0.05 mV, or new T-wave inversions)

OR

3. Development of new, abnormal Q waves (>30 msec in duration and >1 mm in depth) in >2 contiguous precordial leads or >2 adjacent limb leads; or increase R amplitude in V1-V3 consistent with posterior infarction

OR

4. Pathologic findings of an acute MI.

B. **Spontaneous MI (Elevated biomarkers)** - For patients with no recent revascularisation in whom biomarkers from a qualifying (or recent) MI remain elevated, criteria 1 and 2, or criterion 3, or criterion 4 must be met:

1. Cardiac biomarker re-elevation defined as:

- (a) Increase by at least 20% of the previous value; and

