# **1.6 Definition of Cardiovascular Death**

Cardiovascular death includes sudden cardiac death, death due to acute myocardial infarction, death due to heart failure, death due to stroke, and death due to other cardiovascular causes, as follows:

- 1. **Sudden Cardiac Death**: refers to death that occurs unexpectedly in a previously stable patient and includes the following deaths:
  - (a) Witnessed and instantaneous without new or worsening symptoms
  - (b) Witnessed within 60 minutes of the onset of new or worsening cardiac symptoms
  - (c) Witnessed and attributed to an identified arrhythmia (eg, captured on an electrocardiographic (ECG) recording or witnessed on a monitor by either a medic or paramedic)
  - (d) Patients unsuccessfully resuscitated from cardiac arrest or successfully resuscitated from cardiac arrest but who die within 24 hours without identification of a non-cardiac etiology
  - (e) Unwitnessed death or other causes of death (information regarding the patient's clinical status within the week preceding death should be provided)
- 2. **Death due to Acute Myocardial Infarction**: Death occurring up to 14 days after a documented acute myocardial infarction [verified either by the diagnostic criteria outlined for acute myocardial infarction or by autopsy findings showing recent myocardial infarction or recent coronary thrombus] and where there is no conclusive evidence of another cause of death.

If death occurs before biochemical confirmation of myocardial necrosis can be obtained, adjudication should be based on clinical presentation and ECG evidence.

Death due to a myocardial infarction that occurs as a direct consequence of a cardiovascular investigation/procedure/operation will be classified as death due to other cardiovascular cause.

- 3. **Death due to Heart Failure or Cardiogenic Shock**: refers to death occurring in the context of clinically worsening symptoms and/or signs of heart failure without evidence of another cause of death. New or worsening signs and/or symptoms of congestive heart failure (CHF) include any of the following:
  - (a) New or increasing symptoms and/or signs of heart failure requiring the initiation of, or an increase in, treatment directed at heart failure or occurring in a patient already receiving maximal therapy for heart failure.

- (b) Heart failure symptoms or signs requiring continuous intravenous therapy or oxygen administration
- (c) Confinement to bed predominantly due to heart failure symptoms

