- (d) Pulmonary oedema sufficient to cause tachypnea and distress not occurring in the context of an acute myocardial infarction or as the consequence of an arrhythmia occurring in the absence of worsening heart failure
- (e) Cardiogenic shock not occurring in the context of an acute myocardial infarction or as the consequence of an arrhythmia occurring in the absence of worsening heart failure.

Cardiogenic shock is defined as systolic blood pressure (SBP) < 90 mm Hg for greater than 1 hour, not responsive to fluid resuscitation and/or heart rate correction, and felt to be secondary to cardiac dysfunction and associated with at least one of the following signs of hypoperfusion:

- Cool, clammy skin *or*
- Oliguria (urine output < 30 mL/hour) *or*
- Altered sensorium *or*
- Cardiac index  $< 2.2 \text{ L/min/m}^2$

Cardiogenic shock can also be defined as  $SBP \ge 90 \text{ mm Hg}$  as a result of positive inotropic or vasopressor agents alone and/or with mechanical support in less than 1 hour.

The outcome of cardiogenic shock will be based on CEC assessment and must occur after randomisation. Episodes of cardiogenic shock occurring before and continuing after randomisation will not be part of the study endpoint.

This category will include sudden death occurring during an admission for worsening heart failure.

4. **Death due to Cerebrovascular Event** (intracranial hemorrhage or nonhemorrhagic stroke): refers to death occurring up to 30 days after a suspected stroke based on clinical signs and symptoms as well as neuroimaging and/or autopsy, and where there is no conclusive evidence of another cause of death.

Definition of Death due to Stroke: refers to death occurring up to 30 days after a stroke that is either due to the stroke or caused by a complication of the stroke.

5. **Death due to Other Cardiovascular Causes**: death must be due to a fully documented cardiovascular cause not included in the above categories (eg, dysrhythmia, pulmonary embolism, or cardiovascular intervention).

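### MI and ischaemic stroke are analysed as components only in non-fatal form, so a treatment difference in case fatality could pass for a difference in MI or stroke risk

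*Protocol*

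**What the plan says.** Section 2.2.2 sets as an objective a reduction in "The individual components of the primary endpoint (CV death, non-fatal MI or non-fatal ischaemic stroke"). Section 12.1.3.3 turns this into separate endpoints: CV death, non-fatal MI, and "Non-fatal ischaemic stroke". On the form of analysis it says "Other efficacy endpoints include the time to the first event for the first 11 bullet points", and the three components are among those 11. The synopsis and section 6.3.3 carry the same list. None of them has an endpoint of MI or ischaemic stroke whether fatal or not.

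Appendix G handles survival differently in different places:

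- Section 1.1 does not require survival: "All myocardial infarctions (MIs) will be counted as events whether they represent the reason for the hospitalisation or occurred during a hospitalisation". Its universal-definition classes include type 3, which is fatal by definition. The stroke definition in section 1.2 includes strokes that kill within 24 hours.
- Section 1.6 assigns deaths to causes. Death due to MI is "Death occurring up to 14 days after a documented acute myocardial infarction" without conclusive evidence of another cause. Cerebrovascular death "refers to death occurring up to 30 days after a suspected stroke" and includes intracranial haemorrhage. Death from a procedure-related MI is filed under other cardiovascular causes.
- No section says how long a patient must survive for an MI or stroke to be non-fatal.

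**The concern.** Inside the composite the word non-fatal does little harm, because CV death picks up the fatal events. As a stand-alone endpoint it makes counting depend on something that happens after the event. On the plain reading the most severe MIs and strokes drop out of the MI and stroke lines, and the treatment contrast mixes two quantities: how often events occur and how often they kill.

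The mixture misleads in an awkward direction. If MIs on saxagliptin were equally frequent but more lethal, non-fatal MI would appear to fall. If they were less lethal, it would appear to rise. CV death alongside does not resolve this, because it pools sudden, MI, heart failure, cerebrovascular, other and presumed CV deaths. Readers use component results to see what lies behind the composite, which here serves both the efficacy and the safety objective.

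**Working it through.** **1. The plan's own figure.** The protocol gives no figure for the MI or stroke components. Its stated figure is 1040 primary events for 85% power at HR 0.83, 1-sided 2.45%, 1:1 allocation (section 12.3). By Schoenfeld's formula, events = 4(z_α + z_β)² / (ln HR)² = 4(1.969 + 1.036)² / (ln 0.83)², which is 1041. Power with 1040 events is 0.850. Power against the 1.30 margin at a true HR of 1 is 0.988, consistent with the stated minimum of 98%. These figures reproduce, and the point below does not touch them.

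**2. Formula for the components.** Let the total MI hazard be λ in both arms, so the true HR for MI is 1. Let a fraction f0 of MIs be fatal on placebo and f1 on saxagliptin. The hazard of a non-fatal MI is λ(1 − f0) or λ(1 − f1), so

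HR(non-fatal) = (1 − f1) / (1 − f0).

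The same holds for ischaemic stroke.

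**3. Numbers.** Case fatality is not in the document. The values below are assumptions, with f1 = k × f0.

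| Placebo f0 | k | Saxagliptin f1 | HR(non-fatal) |
|---|---|---|---|
| 10% | 0.5 | 5% | 0.95/0.90 = 1.056 |
| 10% | 1.5 | 15% | 0.85/0.90 = 0.944 |
| 20% | 0.5 | 10% | 0.90/0.80 = 1.125 |
| 20% | 1.5 | 30% | 0.70/0.80 = 0.875 |
| any | 1 | f0 | 1.00 |

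**4. Does the method of analysis matter?** A simulation used 2,000,000 patients per arm, an assumed MI hazard of 1.0% and other-death hazard of 1.2% per year, follow-up of 3 to 4.25 years, and case fatality of 20% against 30%. The cause-specific HR for non-fatal MI was 0.872 and the cumulative-incidence ratio was also 0.872, against 0.875 from the formula. The HR for total MI was 1.000. The shift comes from the endpoint definition, so neither a different censoring rule nor a competing-risk model removes it.

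**5. Precision.** Leaving out 10-20% of events widens the confidence interval for the log HR by 1/√0.90 = 1.054 to 1/√0.80 = 1.118, about 5-12%, relative to total events. This does not depend on case fatality differing between arms.

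**6. Chance of a misleading result.** Take an assumed 300 to 500 total MIs and case fatality of 20% against 30%. That leaves 300 × (0.80 + 0.70)/2 = 225 to 375 non-fatal MIs. The chance of a nominally significant benefit at 1-sided 0.025 is then about 17-25%, although total MI risk is equal.

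**The case against.** **The protocol does not say that fatal events are removed.** A reader might infer that a patient who dies within 14 days of an MI, or 30 days of a stroke, is censored in the component analysis. The documents do not support stating this as fact. Those windows define cause of death, not the term non-fatal. Section 11.1 says that "the time from randomisation to event or time to last documented contact for patients with no event will be calculated", but writes this for the primary and secondary endpoints and does not extend it to the other efficacy endpoints. Appendix G 1.1 counts all MIs, so an MI and a CV death some days later might each be counted in its own line. This stands. It leaves an ambiguity rather than a solution: on the plain reading survival decides the count, and on the other reading the label disagrees with the definition.

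**The components match the objective.** Section 2.2.2 promises the components of the composite as defined, and 12.1.3.3 delivers them. This also stands. It is a reason to add analyses, not to replace those listed.

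**The impact is limited.** The components lie outside the test sequence in section 12.2.2-12.2.3 and its type I error rules. Fatal MI and stroke enter both composites through CV death, and all-cause mortality is a formal secondary endpoint. More lethal MIs would tend to raise CV death, so the signal would not be wholly hidden. All true, although the pooled CV death line cannot show where such a signal comes from.

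**The size is hypothetical.** The protocol gives no case fatality and no reason to expect it to differ between arms. With equal case fatality the shift is zero.

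**Conclusion.** The point holds as a modest, inexpensive improvement to non-confirmatory endpoints. The listed MI and stroke components cannot, on the plain reading, separate risk of the event from risk of dying of it, and the term that decides this is undefined.

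The HR range of about 0.88-1.13 rests on three assumptions: equal total incidence, placebo case fatality of 10-20%, and case fatality halved or raised by half on saxagliptin. It shows what could happen and does not predict a bias in this trial. It would also be wrong to infer that the superiority test, the first secondary composite or the 1.30-margin test is biased, because all of them count fatal MI and stroke through CV death.

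**What to change.** In section 12.1.3.3, beside the listed non-fatal components:

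- Add time to first MI (fatal or non-fatal) and time to first ischaemic stroke (fatal or non-fatal), and base statements about MI or stroke risk on these.
- Identify fatal events by linking the adjudication committee's cause of death to the adjudicated MI type and stroke subtype. Cause-of-death categories alone are not enough: include procedure-related MI deaths, which Appendix G 1.6 files elsewhere, and exclude haemorrhagic stroke deaths.
- State how an MI or stroke followed by death is counted in the non-fatal lines.

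The committee already adjudicates these events (section 12.4.1), so no new data collection is needed. The cost is the linkage rule, two extra models and a footnote that total-event counts do not sum to the composite. The remedy is incomplete: some rapidly fatal MIs will be classed as sudden or presumed CV death and still be missed, so the total-MI HR is free of the case-fatality effect only as far as fatal MIs are identified.
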